5.2 Recruitment Methods

Aim 1

This is a data analysis study of VINCI-CDW data. We will access the health records of all enrolled Veterans at the VA since February 2020.

Aim 2

Sample size: We anticipate 600-700 surveys per COVID-19 wave, in each of 3 waves, for a total of up to 3,000 Veterans surveyed.

Subject identification/recruitment: Our specific approach to recruitment here (after eligible Veterans are identified) is an exact replication of what we have done successfully in VA Ann Arbor studies including ResCU 1, ResCU 2 (IIR's 13-079 and 17-045, Protocols 1597244 and 1597246). This approach has been repeatedly reviewed and approved by VA Ann Arbor's IRB, most recently May 2021. It is also being used in parallel studies outside VA that have been reviewed in detail by the University of Michigan and Vanderbilt University's IRBs, acting as the central IRB for the National Institutes of Health's COVID-19 follow-up studies.

This approach emphasizes balancing two key competing needs: (a) giving Veterans the opportunity to contribute to research and be heard; with (b) not pestering or coercing Veterans. As evidence that this approach strikes the correct balance, we note that in ResCU 1, 96% of all follow-up calls were completed. We interpret this specific data point—as well as the numerous positive comments from participants—to mean that they appreciated the opportunity to contribute. We heard over and over again that they were eager to participate in follow-up calls

because they enjoyed the first call and were glad that VA and NIH were interested in hearing their perspective. Our use of highly trained surveyors, including both Veterans and COVID-19 survivors, is crucial to providing the respectful environment that makes this possible.

Thus, we will utilize existing data from Aim 1 to identify subjects for recruitment, as outlined above. Aim 1 has been approved with a HIPAA waiver and full waiver of informed consent.

Those selected will be mailed a recruitment letter (with an option to opt out) and research information sheet describing the study, 1-2 months before the first planned survey. We will then follow-up with a phone call to discuss the study with those who do not opt out from further contact. Before each contact attempt, we will check CDW to ensure the Veteran is still alive and is not hospitalized. We will also use VHA's national electronic medical record (EMR), by way of VistaWeb and JLV.

In light of past practices and experiences, we have learned that it is important to Veterans and other patients to try a range of call times, and give them multiple opportunities to participate. In a recent study of patients recovering from respiratory failure by our group—reviewed and approved by Vanderbilt's IRB and an NIH Data Safety and Monitoring Board—it required a median and [interquartile range (IQR)] were 6 [3-13], 4 [2-10], 5 [2-11] calls to find a time when it was convenient for participants to complete the survey at 3-months, 6-months and 12-months respectively. Other studies conducted by our long-term outcomes survey team have shown similar results. In a study of patients recovering from infection, it required a median and [interquartile range (IQR)] of 2 [1-3], 3 [1-4], 2 [2-4] calls to find a time that was convenient for participants to complete the survey at 1-month, 3-months, and 6months post-hospital discharge. In a study of patients with sepsis-induced hypotension, a median and [interquartile range (IQR)] were 4 [2-8] and 3 [2-6] calls to find a time that was convenient for participants to complete the survey at 6-months and 12-months. Again, the 80-90% repeated participation by these cohort members (as well as their comments to us) suggest this call intensity was viewed as providing flexible opportunities to participate, rather than being unwelcome. We need to be very explicit—the higher number in the interquartile range means that 1 in 4 participants who completed a survey required more than that number of calls to participate. Our analyses suggest that survivors with less education require more calls, in part because of their more variable work schedules. Setting a limit on calls too low will systematically exclude participants, particularly less educated participants, from the ability to contribute to their fellow Veterans' recovery.

Our approach to contacting Veterans who do not opt out is informed by these data, and informed by our study team members who include a COVID-19 survivor and a Veteran who has a long experience doing peer support to other Veterans. We will attempt to contact Veterans who do not opt out up to 12 times to obtain informed consent, only leaving messages 3 of those times. We will *always* cease contact at the Veterans' request, at any time; if they do not provide informed consent within the 12 contact attempts, we will also cease. If a Veteran does not respond after 7 call attempts, we will send a Consent Contact Letter to the Veteran, which will count as 1 of our 12 contact attempts. We will then make 4 more call attempts if needed. After answering all of their questions about the study, we will obtain verbal informed consent from those who agree to participate in the study and then proceed with the survey. Veterans will be reminded that they can stop the survey at any time with no adverse consequences for them. When telephone administration is not feasible, we will offer REDCap-administered web-based surveys or mail surveys.

When Veterans cannot complete the survey themselves, we will contact their proxy as indicated by the Veteran. We will follow similar recruitment procedures for the proxy (i.e. mail a recruitment letter and information sheet then follow-up via phone). Please see the Proxy Protocol for more detailed information. Any identifiable information collected for Proxy's will be stored in Access.

Participant Incentives: Our specific approach to recruitment here is an exact replication of what we have done successfully in VA Ann Arbor studies including ResCU 1, ResCU 2 (IIR's 13-079 and 17-045, Protocols 1597244 and 1597246). Veterans will be mailed a \$10 gift card for each survey to which they answer any questions at 12, 18,

24, 30, and 36 months, totaling up to \$40 (Note: not all COVID-19 waves will be eligible for all surveys waves, as per Table 3 above).

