A driving finding in VA research for the last decade has been that there is unequal and incomplete access to the benefits of VA care. EHR data by definition are only available for Veterans who have accessed care in the VA, including VA community-based care and contracted care. Other Administrative data (e.g., claims data for Medicare, Medicaid) are not available in real-time, given our dependency on other entities (i.e., CMS and VIReC) for production and linkage. Further, many important measures are not systematically ascertained or entered into the EHR in a uniform fashion for all patients. Therefore, prospective primary data collection from Veterans is necessary to define measures that are poorly captured in the VA EHR including care received at non-VA sites, caregiving receipt, disability, and employment/role function and financial toxicity, and unmet care needs in order to ensure the relevance of the work being done here. In general, we will seek to survey Veterans at 12, 18, 24, 30, and 36 months after their initial SARS-CoV-2 infection, enrolling new patients as the epidemic continues, and following patients longitudinally. The key variables of interest from new survey data for the LTO are shown in Table 2 below.

Concept	Instrument	# of items (Approx)			
Activity + Quality of Life	Activities of Daily Living (ADL) and Instrumental Activities of Daily Living (IADL); EQ-5D-5L	18			
Participation	Life Space Mobility	9+			
Employment	Health and Retirement Study's Job Status Form	1			
Financial Toxicity	NHLBI COVID-19 Financial Toxicity scale	10			
Mental Health	PHQ-9 Depression Symptoms scale	9			
Unmet Need	PROMISE instrumental support	4			
Non-VA Healthcare	VIREC Utilization Measures	2			
Fatigue + Symptoms	PROMIS Fatigue Short Form 7a; open-ended questions	9			

Aim 2 Study Population: The population of Veterans eligible for random sampling into the survey will be the same as those eligible for inclusion in Aim 1. Therefore, all data from Aim 1 will be linkable to survey responses via a cross walk.

Cases: Our primary case definition are Veterans infected with SARS-CoV-2, as defined by the standard locally available test at the time of their infection, and identified within the COVID-NST. We will restrict to Veterans seeking primary care in VA. Viral infection index date will be defined as the date of sample collection for each

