patient's first positive test. We will conduct stratified random sampling with differential survey weights so that cases are equally divided based on maximal severity of their acute COVID course in VA to include members of the following mutually exclusive groups based on patterns of health care utilization within the first 30 days after initial infection with SARS-CoV-2: not hospitalized in VA; hospitalized in VA but not mechanically ventilated; mechanically ventilated. Stratified random sampling with variable sampling weights offers two advantages: (1) sampling weights assure that the aggregated population results are still representative of the study population as a whole; while (2) ensuring adequate representation to support comparisons across these subgroups of interest. Stratum- and wave-specific sampling fractions will be chosen based on data on survival to the relevant time-point in.

In general, we will organize the sampling of cases (and later of comparators) around the waves of the epidemic, as defined by their nadirs between national death rates—each approximately 3-4 months long, as shown in Figure 2 generated based on data from the COVID tracking project. As shown in Table 3, we will initiate surveys of Veterans who have survived their initial SARS-CoV-2 infection. The viral infection "index date" will be defined as date of each patient's first positive test. This will be a longitudinal survey such that once we start surveying a Veteran, that same Veteran will be surveyed in later waves as well—we will not "resample" between, for example, the 12- and 24-month surveys.

Comparators: To support causal inference, we will also sample Veterans without COVID who are matched to participants with COVID-19. In general, cases will be compared to comparators matched on risk of developing COVID infection during a given wave, incorporating geography at the VAMC and VISN level to take into account spatiotemporal heterogeneity and small area variations. There are certain nuanced issues around precise definitions of pseudo-index dates for comparators, and particularly avoiding immortal time bias, to which we will closely attend during implementation with the input of the Methods Core. In general, we will use coarsened exact matching or propensity scores to ensure balance on key measurable covariates, both of which our group has substantial experience with.

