Table 3: Example of a Timeline of Cohorts for Survey Operations. Dates on the left indicate when the COVID-19 infection occurred. Dates on the top indicate when the survey would be done. Blocks of similar surveys are shaded. The numbers 12, 18, 24, etc. represent how many months after infection each survey is, to evaluate longitudinal changes over time.

			CORC	Calenda	r Time						year 2	->											year 3-	.>	
			2021				2022												2023						
COVID Infection Date			Septer	Octobe I	Vovem	Decem	Januar	Februa	March	April	May	June	July	Augus	Septe	Octob	Novem	Decem	Janua	Februa	March	April	May	June	July
2020	March	400 COVID	18	18					24	24					30	30					36	36			
"Vanguard"	April	200 Comparison		18	18					24	24					30	30					36	36		
	May	Each Surveyed 4x			18	18					24	24					30	30					36	36	
	June	Lacii Surveyeu 47	•			18	18					24	24	ı				30	30					36	36
	July																								
"Summer"	August																								
	September																								
	October																								
"Predictable"	November	400 COVID			12	12					18	18	}				24	24							
		200 Comparison				12	12					18	18	3				24	24						
2021	January	Each Surveyed 3x					12	12					18	18	3				24	24					
	February	Lacii Surveyed 3x						12	12					18	18					24	24				
	March	400 COVID							12	12					18	18					24	24			
"Early Vaccine Era"	April	200 Comparison								12	12					18	18					24	24		
	May										12	12	!				18	18					24	24	
	June	Each Surveyed 3x										12	12	2				18	18					24	24

Sample Size: We will enroll up to 3,000 Veterans over the course of the survey, interviewing them each 2-4 times. This sample size is driven by power calculations needed to examine key subgroups of interest, including looking for differences across waves of COVID-19, and in racial and gender minority groups of keen interest to the VA's mission. Taking this sample size into consideration, our selection of measures emphasized continuous or multivalued outcomes over binary outcomes to increase statistical power.

Survey operations: Our primary survey administration mode, as in past work, will be computer-assisted telephone administration by highly trained surveyors using highly validated instruments. When telephone administration is not feasible, we will offer REDCap-administered mail surveys.

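### Protocol 5.2 gives up to 3,000 Veterans as the total of three waves of 600-700, which come to 1,800-2,100, and 5.1 ties its power rationale to 3,000

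*Protocol*

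**What the plan says.** The Aim 2 sample size appears in two places in the protocol.

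- Section 5.2 (Recruitment Methods): "We anticipate 600-700 surveys per COVID-19 wave, in each of 3 waves, for a total of up to 3,000 Veterans surveyed".
- Section 5.1 (Study Design, Sample Size): "We will enroll up to 3,000 Veterans over the course of the survey, interviewing them each 2-4 times". The next sentence begins "This sample size is driven by power calculations needed to examine key subgroups of interest, including looking for differences across waves of COVID-19" and goes on to name racial and gender minority groups. The paragraph ends: "Taking this sample size into consideration, our selection of measures emphasized continuous or multivalued outcomes over binary outcomes to increase statistical power".

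Three other statements in 5.1 bear on the count.

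- Table 3 is captioned "Example of a Timeline of Cohorts for Survey Operations". It fills in three waves (Vanguard, Predictable and Early Vaccine Era), each with 400 COVID and 200 comparison Veterans. The first is surveyed four times; the other two are marked "Each Surveyed 3x". The Summer row carries no sample.
- Follow-up is longitudinal: "once we start surveying a Veteran, that same Veteran will be surveyed in later waves as well".
- The Aim 2 design also foresees "enrolling new patients as the epidemic continues", without a number.

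Neither the protocol nor the SAP gives a significance level, power, effect size or standard deviation for the power calculations that 5.1 mentions.

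**The concern.** The sentence in 5.2 reads as a sum: a number per wave, a number of waves, and a total. The total does not follow from the other two. A loose upper limit in a recruitment section would matter little by itself. It matters here because 5.1 treats the same number as the design size, saying both that power calculations led to it and that the outcome measures were chosen with it in mind.

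A reader who wants to judge whether the survey can support comparisons between waves, or within racial and gender minority groups, has only this statement to go on. That reader cannot tell whether the calculations assumed 3,000 Veterans or the 1,800-2,100 that the waves supply.

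**Working it through.** **Inputs.** 600-700 per wave, 3 waves and a stated total of 3,000 (5.2); 400 COVID plus 200 comparison Veterans in each of three populated waves, surveyed 4, 3 and 3 times (Table 3 in 5.1); the same Veterans surveyed again without resampling (5.1).

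**Step 1: try to reproduce the stated total.**

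- Total = waves x number per wave.
- Lower end: 3 x 600 = 1,800.
- Upper end: 3 x 700 = 2,100.
- Table 3: 3 x (400 + 200) = 1,800, made up of 3 x 400 = 1,200 COVID and 3 x 200 = 600 comparison Veterans.

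The stated 3,000 is not reproduced. Table 3 agrees with the lower end of the range in 5.2.

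**Step 2: size of the gap.**

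- 3,000 - 2,100 = 900 and 3,000 - 1,800 = 1,200 Veterans.
- 3,000 / 2,100 = 1.43 and 3,000 / 1,800 = 1.67.

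**Step 3: see whether another reading yields 3,000.**

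| Reading | Arithmetic | Result | Fit with the text |
|---|---|---|---|
| Counting survey administrations | 600 x (4 + 3 + 3) | 6,000 | Overshoots, and repeat surveys add no Veterans |
| Adding a Summer wave | 4 x 600 to 4 x 700 | 2,400-2,800 | Falls short, and 5.2 says three waves |
| More waves of 600 | 5 x 600 | 3,000 | Matches, but 5.2 says three waves |
| Larger waves | 3,000 / 3 | 1,000 per wave | Above the 600-700 stated |
| 600-700 are cases only, comparators added at Table 3's 2:1 ratio | 3 x (600 + 300) to 3 x (700 + 350) | 2,700-3,150 | Spans 3,000, but Table 3 has 400 cases per wave and counts the comparators within the 600 |

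Two readings fit 3,000 without changing the per-wave figure: five waves of 600, and cases plus comparators. The first conflicts with the number of waves in 5.2 and the second with the make-up of a wave in Table 3.

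**Step 4: power.** No power formula can be run, because none of its inputs is stated. The text therefore cannot show which N the calculations used.

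**The case against.** The strongest reply is that both sections say *up to* 3,000. In a protocol written for an ethics board, an enrolment maximum above the expected number is ordinary, and 1,800-2,100 lies within it. Room to grow is also signalled. Table 3 is only an example, 5.1 expects new enrolment as the epidemic goes on, and the introduction explains that not all of the research could be planned in advance. On this view the expected size and the limit are two separate statements that merely share a sentence.

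Much of this stands. No limit is exceeded, and 3,000 may have been meant as headroom or may reflect further waves. But the reply does not account for 5.1. There the only number that the power sentence can refer to is 3,000, and a power rationale has to attach to the size that is expected to be analysed, not to a maximum well above it. Nor does 5.2 leave the number of waves open: it says three, and no section gives a size for any further wave.

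A second reply is that nothing downstream depends on the figure. For the SAP that is correct. The SAP reports its own sample (600 Veterans with COVID-19 sampled, of whom 235 completed surveys, and 244 comparators) and uses neither 3,000 nor 2,100. Its model tests a COVID-by-time interaction with adjustment for age, sex and CAN score, and has no wave, race or gender subgroup test. The point therefore concerns the protocol's stated rationale and not the planned analysis.

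**Conclusion.** The inconsistency is real and limited in scope. The stated waves give 1,800-2,100 Veterans, and the protocol names 3,000 as their total and as the size that power calculations led to, which is 1.43 to 1.67 times as many. This rests on reading 600-700 as Veterans per wave with comparators included, as Table 3 does. The documents do not show whether the total, the per-wave number or the wave count is the figure to correct.

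A reader might infer that the subgroup comparisons are underpowered by the corresponding factor. The documents do not support that. The power inputs are absent, so the N behind the calculations is unknown. The effect would also depend on where the extra Veterans were to come from. Larger waves would mean 1,000 per wave instead of 600-700, whereas more waves would leave the size of each wave, and hence a contrast between two given waves, unchanged. Nor can it be inferred that an enrolment limit was exceeded or that the SAP analysis is compromised.

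**What to change.** In 5.1 and 5.2, give the planned size as 1,800-2,100 Veterans (three waves of 600-700, comparators included), and note that the Table 3 example corresponds to 1,800. Describe 3,000 as a maximum only if the sponsor confirms that this is what it is. If 3,000 is the planned size, state instead the additional waves or the per-wave numbers that produce it, and bring Table 3 into line.

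Then attach the power sentence in 5.1 to the size actually planned and say which N the calculation used. If that cannot be documented, withdraw the claim that the planned size is power-driven.

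The cost is two or three sentences, with no further enrolment and no change of analysis. The downside is a less favourable stated size, and the loss of the power claim if it cannot be tied to 1,800-2,100.

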5.3 Informed Consent Procedures

Aim 1

This study is a secondary analysis of data of approximately 8 million electronic VA health records. It would not be feasible to contact and subjects to obtain informed consent.

Aim 2

All local site study personnel will be trained regarding human subjects protections requirements and how to obtain and document informed consent for the aims outlined below.

- We are requesting a waiver of documentation of informed consent.
- Those selected will be mailed an information sheet describing the study, and a recruitment letter with an invitation to participate, including an opt-out option, 6 months after index illness. We will then follow-up with a phone call to discuss the study with those who do not opt out from further contact. Approved study team members will obtain verbal consent from those who agree to participate in the study and then proceed with the survey. Agreement to participant in this study will be documented in REDCap. Our specific approach to recruitment here is an exact replication of what we have done successfully in VA Ann Arbor studies including ResCU 1, ResCU 2 (IIR's 13-079 and 17-045, Protocols 1597244 and 1597246).
- All hard copy records will be maintained in a locked cabinet in the research team's locked office.
 Computerized data will be stored in an electronic folder maintained on the VA Server or behind the VA Firewall, here: I:\[name] CORC LTO. Only approved and trained study team members will collect and have access to study data. Only aggregate study data will be shared.

We will ask participants if they agree to the storage, sharing, and use of their research data for future use in research studies related to COVID-19 infection and other health conditions. Researchers that access this data for future research use may be national or international and affiliated or unaffiliated with the VA, and may only use the data for research purposes. Future studies will have appropriate data use agreements in place as well as receive approval by an IRB and other oversight committees prior to starting any research. This specific approach, including the language used to inform the Veteran and of their option to opt-out, is taken directly from the VA' Cooperative Studies large "EPIC3" study of biosamples in COVID-19. We note that we will *not* have linked biosamples, yet still use their stringent approach to requesting permissions. Please see the Data Repository section on page 25 for additional details.

5.4 Inclusion/Exclusion Criteria

Inclusion:

 All VA enrollees since February 2020, which includes all patients who were tested for SARS-CoV-2 and are included in the VA COVID-19 Shared Data Resource in CDW.

Exclusion:

VA employees

5.5 Risk/Benefit Assessment

Aim 2 Risks: This is a minimal risk study. Federal regulations at 45 CFR 46.111(a)(1) require that risks to subjects are minimized by using procedures which are consistent with sound research design. There are no study procedures, and there are no consent forms that pose a potential risk to privacy. Potential risks for this study include breach of confidentiality. All data will be collected and stored securely:

- Protected Health Information: we are requesting a HIPAA authorization waiver for the screening portion of this study. We will collect Veteran contact information to contact them for surveys and interviews, as well as social security numbers and medical record numbers. This PHI will only be kept on Microsoft Access behind the VA firewall in a protected folder, here I:\[name] CORC LTO, or on VA REDCap.
- Survey Data: Survey data will not contain identifiable information. We will use REDCap to collect and temporarily store survey-based data, and other non-identifiable administrative data, such as consent date, survey date, and information related to refusal/exclusion/withdrawal. This data will be collected via the VA REDCap service by approved study team members at AAVA. We will use arbitrary study IDs to link a Veteran's identifiable information with the information we collect via REDCap. Data will be downloaded on a weekly basis to a protected folder, here I:\[name] CORC LTO.

Performing this study under waiver of documentation of informed consent for Veterans will minimize risk to privacy, as there will be fewer paper records that have potential to cause a security breach.

Our efforts to protect privacy and respond to survey respondent distress are based on years of experience using specific approaches that are an exact replication of what we have done successfully in VA Ann Arbor studies including ResCU 1, ResCU 2 (IIR's 13-079 and 17-045, Protocols 1597244 and 1597246).

To minimize the risk of a breach of confidentiality, we will perform the following steps. First, as soon as the cohort is defined by the data manager, each patient in the cohort will be assigned a unique study ID. We will then create a password protected electronic tracking file that maps the study participant's identifying information to the study ID. No identifying information will be placed on data collection forms (e.g. surveys). Identifiers of potential recruits and study participants will be required to allow for follow-up contacts and to link data from different sources during the data collection phase. These will be kept in password protected files for the duration of the project and will then be destroyed according to VHA Records Control Schedule 10-1 (RCS 10-1) once direction for destruction of research records is published by VHA. Electronic data will be maintained behind a secure firewall maintained by the Ann Arbor coordinating center, here I:\[name] CORC LTO. All identifiable data will be kept behind the firewall, with access only available to key study team members. The data manager will be responsible for creating analytic datasets for statisticians and investigators; these datasets will be de-identified per HIPAA guidelines. All resulting research data will be presented in aggregate only. Furthermore, study staff sign a pledge of confidentiality and understand that breach of confidentiality is grounds for dismissal. Study staff are required to complete annual training on privacy and HIPAA, as well as triennial training on human subjects protection. Access to participant data, both paper and electronic, will be given to VA project staff only and on an "as-needed" basis. There are no treatments, procedures, or interventions as part of this study. Any complaints/concerns expressed to the study staff by participants, providers, or anyone else affected by this study will be immediately reported to the PI and IRB, as will any unexpected events.

If a participant becomes distressed, the research staff will intervene as appropriate (i.e., comfort the participant and/or seek assistance from the PIs). All contacts and interviews will be conducted in a sensitive manner that protects the dignity of respondents. Research staff working with participants will be trained for situations in which a respondent expresses the need for help with a personal or emotional problem. If a respondent verbalizes this, the research team member will ask if he or she would like the contact information for a Veteran's help line. If the respondent wants such information, the staff member will provide it. In the event that a participant expresses

suicidal or homicidal ideation, or other serious psychiatric or medical symptoms, the PI will be notified immediately and advise the research staff member as to the most appropriate course of action (i.e. contacting appropriate authorities such as a mental health professional or police). Staff will follow the protocol for PHQ-9 suicidality assessment should a patient indicate suicidal thoughts while completing the PHQ-9 (see Protocol for PHQ-9 for more information). All project staff will have been trained on VA's suicide risk assessment and response guidelines, including the capability of directly connecting suicidal participants to the 24-hour VA suicide hotline.

We wish to draw attention to this approach to participant distress or suicidality because we believe it represents a particular strength of our group, both our personnel and standard operating procedures. Our team of interviewers are long-term career professionals with substantial training and experience; they include Veterans and COVID-19 survivors to insure those perspectives are baked into everything our team does. We have published our approach to safely handling disclosure of suicidal ideation in the peer reviewed literature⁴⁷, and pride ourselves on being able to ensure Veteran safety is always the highest priority.

Aim 2 Benefits: there are no direct benefits from participating in this study. Contributing to this science may build a better understanding of the long-term impacts of COVID-19 on Veterans.

